### **Method of Assigning Subjects to Treatment Groups**

At enrollment and after an ICF is signed, subjects will be identified by their subject ID. Subjects with severe alcoholic hepatitis will be screened for this trial from the inpatient services of the participating centers. Informed consent will be obtained after confirming eligibility. Baseline studies will be performed and subjects will be started on prednisolone/prednisone (40 mg/day) and randomized to the study drug 2400 mg, 4800 mg/day, or placebo. Once enrolled at the Screening visit, each subject will be given a unique identification number which will identify both the site and the individual subject. At the time of randomization, the randomization code will be linked to this identifier and this information will be provided to the clinical center by the data coordinating center. This information will be used by the investigational drug pharmacy to dispense the appropriate study drug/placebo to the individual subject.

Subjects will be randomized sequentially, as they become eligible for randomization. If a subject discontinues participation from the study, their unique identifier code will not be reused, and the subject will not be allowed to re-enter this study.

The appearance and packaging of active and placebo powders for reconstitution are identical. Sachets of study drug will be packed in groups of two sachets into sealed cardboard boxes supplied by Immuron Ltd. Each box will have a code which will be matched to the randomization code at the data coordinating center. Following reconciliation of the randomization code with the box code, the investigational drugs pharmacy will dispense enough medication to last 28 days (56 packs, a total of 112 sachets).

A sealed master list of “box codes i.e. the box set number” vs. randomization code will be securely held by Immuron Ltd., the data coordinating center and also in a sealed envelope by each site pharmacy.

To maintain the double-blind design, drug supplies will be dispensed only by the investigational drug pharmacist, according to a written procedure provided by the Sponsor. The pharmacist will not participate in any other study procedure.

### **Randomization Procedures**

This is a double blind study and therefore the study staff and the subjects will remain blinded to the code assignments throughout the study. Prior to administration, each participant will be assigned with an individual number and will be provided with IP packs according to the predetermined computer generated randomization list.

### **Unblinding Procedures**

The Investigator will promptly document and explain to the data coordinating center, the NIAAA and the data safety and monitoring board any premature unblinding (e.g., accidental unblinding, unblinding due to a serious adverse event) of the investigational product(s). Reasons for premature unblinding will be clearly documented by all research personnel involved and will include reason(s) of unblinding. In cases of emergency where written permission cannot be obtained, the site PI will make the decision to unblind based on the perceived harm to the subject if that is not done and then document that unblinding has occurred.

Upon completion of the study, emergency code envelopes will be returned to the Sponsor.

### **Dispensing, Compliance and Accountability**

Eligible subjects will be randomly assigned to each of the study groups. Subject will be instructed to take the contents of two sachets of powder reconstituted with water twice daily. Subject ID pack dispensing will be documented in the Case Report Forms and on the Investigational Drug Administration Records.

To prepare the study drug immediately before administration, add the powder to a cup and add approximately four tablespoons of water to the cup, stir gently for 1 minute until dissolved. Each subject will be required to drink the contents of both sachets in the morning before breakfast. Additional water may be added to the powder to ensure all the powder is taken. Subjects will be required not to eat for 2 hours after taking the drug. If a subject forgets to take the drug in the morning, he/she can take the drug during the day. He/she will be required not to ingest food for

2 hours before and 2 hours after taking the drug. The subject will also be instructed to take the contents of two sachets in the evening, at least 2 hours after eating.

The Investigator/designee is responsible for maintaining accountability for the receipt, dispensing, and return of all study medication.

The Investigational Pharmacy will be responsible for recording the receipt of all drug supplies and for ensuring the supervision of the storage and allocation of these supplies. When a shipment is received, the pharmacist verifies the quantities received and the accompanying documentation (e.g. certificate of analysis, date of manufacturing/expiry, storage instructions etc.) and return the acknowledgment of receipt to the Sponsor.

The Investigator/designee is responsible for keeping records of receipt of study medications, where the study medication is stored after arrival to the clinic and for maintaining detailed records, indicating dates and amounts of drug dispensed to whom ("subject by subject accounting").

Subjects will be requested to return all the used and unused sachets. That shall be recorded by the Investigator/designee in the CRF. The records should:

- distinguish between unopened (not dispensed) and unused (by study subjects) supplies;
- explain broken or lost drug supply; and
- account for all supplies and stock that may have been used.

The subjects will be properly educated about these procedures. If unused drug is returned, the Investigator/designee must follow protocol instructions regarding documentation.

The Monitor will check the drug account, and all unused drug will be sent to the pharmacy or drug depot at the site and destroyed at the end of the study. Products deliberately and/or accidentally destroyed by the Investigator should also be accounted for. Used packs should be kept until the Clinical Monitor has performed drug accountability.

At study termination, unless otherwise specified (in writing), all unused drug supplies, including partially used containers and the study drug accountability log, should be returned to:

Immuron Ltd.

[name]

[name]

[contact]; [contact]

When the supplies are returned, the Investigator or pharmacist signs the Immuron's Investigational Drug Return Form, to verify that all unused or partially used supplies have been returned and that no study supplies remain in the Investigator's possession. One copy of all inventory records and the return statement are retained by the Investigator for the study files.

### **Prior and Concomitant Therapy**

Any concomitant medication should be reported to the study team and will be recorded in the subject's files and CRF.

## Clinical Laboratory

Clinical chemistry and hematology tests will be flagged when outside of the reference range. The responsible Investigator will assess its significance as “Clinically significant” (CS) or “Not clinically significant” (NCS).

Safety tests (biochemistry, hematology, urinalysis and stool analysis: See Table 2) will be performed along with the safety assessment.

Safety tests will be carried out by accredited clinical laboratory. All tests are to be collected and performed according to written instructions. The study coordinator will notify the laboratory when samples have been collected and it is the responsibility of laboratory to pick up these samples on the same day.

Test results will be forwarded to the study team within 48-72 hours.

**Table 1: Protocol Thresholds for Clinical Significance of Abnormal Safety Labs**

Table 1: Laboratory Cutoffs That Would Lead to Drug Discontinuation in an Individual Subject
Hematological 

• Absolute neutrophil count < 500/mm^3

• Platelet count < 20,000/mm^3

Hepatic safety labs 

• AST or ALT > 20x upper limit of normal

• AST or ALT doubling with absolute values > 400 IU/L

Please note that bilirubin is highly elevated to start with and may rise as part of the disease process in subjects with severe alcoholic hepatitis and therefore cannot be used as a test to detect drug induced liver injury
Also, INR is prolonged in subjects with severe alcoholic hepatitis and there cannot be used to evaluate drug related liver injury in this setting

## Evaluation of Adverse Events

Adverse events will be assessed in the scheduled visits (Day 7, day 30, day 90 and day 180), and in unscheduled visits. The intensity of rash, pruritus, malaise, arthralgia and myalgia will be evaluated on a scale of 0 to 3 (see table below) and recorded in the CRF.

### Assessment Scale for Systemic Reaction Severity

Symptoms	Score
Absence of symptoms	0
Slightly bothersome	1
Bothersome and interferes with normal activity	2
Prevents normal activity	3

## Adverse Events

### **Adverse Events (AE), Serious Adverse Events (SAE), and Suspected Adverse Reactions**

An adverse event (AE) is any untoward medical occurrence in a subject participating in a clinical trial. An adverse event can be any unfavorable and unintended sign, symptom or disease temporally associated with the use of the study medication, whether or not considered related to the study medication. AEs will be collected from the start of treatment until 24 weeks following the initial dose of study medication. Any events occurring prior to treatment will be recorded on the medical history page with the event name, onset date and end date if not continuing. Pre-existing, known clinically significant conditions observed at screening should be recorded as medical history.

This definition also includes accidental injuries, reasons for any change in medication (drug and/or dose) other than planned titration, reasons for admission to a hospital, or reasons for surgical procedures (unless for minor elective surgery for a pre-existing condition). It also includes adverse events commonly observed and adverse events anticipated based on the pharmacological effect of the study medication.

A **treatment emergent adverse event** is any adverse event occurring after start of study medication and within the time of residual drug effect, or a pre-treatment adverse event or pre-existing medical condition that worsens in intensity after start of study medication and within the time of residual drug effect.

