**ENDPOINTS:**

*Mechanistic Endpoints:*

- The sample size is based on a decrease in plasma endotoxin levels (adjusting for baseline) as measured by analysis of covariance across the study groups. This was

chosen based on the mechanism of action of Imm 124-E. The hypothesis is that both active-drug groups are superior to placebo. In prior studies, we have found the standard deviation of endotoxin levels to be 8-10%

- markers of gut permeability
- intestinal inflammation (calprotectin)
- TNF- $\alpha$  and other immune-inflammatory markers
- microbiome-metagenome

*Efficacy related endpoints:*

- number of subjects meeting Lille failure criteria at day 7
- mortality at 30 days, 90 days and 180 days,
- time to drop in conjugated bilirubin by 50%
- change in MELD and sequential organ failure assessment scores and Discriminant Function
- serum bile acids
- liver function tests

*Safety related endpoints:*

- incidence and severity of gastrointestinal events, including nausea, vomiting and diarrhea
- Proportion of subjects who develop renal failure, encephalopathy or pulmonary compromise
- Frequency of sepsis
- Frequency of any other adverse events

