## **Risk-Benefit Considerations**

The risk:benefit of Imm 124-E in severe AH has yet to be elucidated. There is a plausible rationale for possible reduction of liver damage secondary to AH but this has not been established. Weighed against these potential benefits are potential risks inherent in the protocol:

1. Like any drug, subjects receiving the drug could experience unanticipated side effects. Based on current experience, Imm 124-E has been well tolerated. Possible side effects of the gastrointestinal tract include nausea, abdominal pain, flatus or diarrhea. It is possible that other, unexpected unanticipated side effects may occur and there may be long latency periods before AEs are detected.
2. There is a possibility of pain and bruising in areas where blood is drawn.
3. If a subject becomes pregnant during the study, there may be risks that are currently unforeseeable that may cause damage to the fetus. The study requires women and men to undertake two forms of contraception.
4. Each subject will be instructed to inform the research physician about any new medical problem that may develop during participation in the study. After the study is completed,

the subjects may contact the study Investigator(s) with any study-related medical problems that may occur.

5. There is a possibility that the immune modulatory effect noted may not have a sustained beneficial effect, or alternatively may exert a deleterious effect on the tested disease parameters.

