### **Secondary Endpoints**

The secondary endpoints will include:

- Frequency, severity and relatedness of adverse events
  - Proportion of subjects with nausea and emesis
  - Proportion of subjects with diarrhea
  - Proportion of subjects who develop renal failure, encephalopathy or pulmonary compromise
  - Frequency of sepsis
- Changes in endotoxin levels adjusted for baseline levels at day 7 and 28
- Change in laboratory parameters

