A **suspected adverse reaction** means any adverse event for which there is a reasonable possibility that the drug caused the adverse event. For the purposes of IND safety reporting, "reasonable possibility" means there is evidence to suggest a causal relationship between the drug and the adverse event. Suspected adverse reaction implies a lesser degree of certainty about causality than adverse reaction, which means any adverse event caused by a drug.

The Investigator is to report all directly observed adverse events and all adverse events spontaneously reported by the trial subject using concise medical terminology. In addition, each trial subject will be questioned about adverse events. The question asked will be "Since you began taking the study medication, have you had any health problems?"

***Procedures for Assessing, Recording, and Reporting Adverse Events and Serious Adverse Events, in Accordance with 21 CFR 312.32(a) FDA Guideline for Safety Reporting***

Throughout the duration of the study, the Investigator will closely monitor each subject for evidence of drug intolerance and for the development of clinical or laboratory evidence of adverse events. All adverse events (expected or unexpected) which occur during the course of the study, whether observed by the Investigator or by the subject, and whether or not thought to be drug-related, will be reported and followed until resolution or until they become stable.

All subjects will be under close medical supervision during their stay in the CRSU or hospital. During the entire course of the study, subjects will be encouraged to report any adverse events which may occur.

Any adverse event or other unwanted response which occurs in the course of the study should be monitored and followed up until:

- It has resolved or stabilized according to the judgment of the Principal Investigator.
- There is a return to normal or baseline values.
- It has been shown to be unrelated to the study drug.

All adverse events noted during the course of the study will be included in the final study report.

The description of the adverse event will include description of event, start date, stop date, intensity, if it was serious, relationship to test drug, change in test drug dosage, if the subject died, and if treatment was required.

Events will be coded to one of the following intensity categories below:

Toxicity Grade	Severity	Definition

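### Pre-treatment symptom intensity is not recorded and the solicited symptom list omits gastrointestinal effects, so the primary safety endpoint loses sensitivity to them

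*Combined protocol and SAP*

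**What the plan says.** **Definition and recorded fields.** The section on adverse events, serious adverse events and suspected adverse reactions gives two routes to treatment-emergent status. One is a new event after the start of study medication. The other is "a pre-treatment adverse event or pre-existing medical condition that worsens in intensity after start of study medication". The same section opens adverse event collection at the first dose and sends anything earlier to medical history, where it is "recorded on the medical history page with the event name, onset date and end date if not continuing".

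**Timing.** Evaluation of Adverse Events and Table 2 place adverse event assessment at Days 7, 30, 90 and 180, plus unscheduled visits. Table 2 has no mark for it at Screening or Day 0.

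**Solicited symptoms.** "The intensity of rash, pruritus, malaise, arthralgia and myalgia will be evaluated on a scale of 0 to 3". The accompanying table is headed as a scale for systemic reactions.

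**Gastrointestinal effects.** Risk-Benefit Considerations states: "Possible side effects of the gastrointestinal tract include nausea, abdominal pain, flatus or diarrhea". The synopsis lists as a safety endpoint "incidence and severity of gastrointestinal events, including nausea, vomiting and diarrhea", and Secondary Endpoints lists the proportions with nausea and emesis and with diarrhea.

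**Elicitation and grading.** Investigators report what they observe and what patients volunteer, and also ask: "Since you began taking the study medication, have you had any health problems". Every reported event then receives an intensity grade of 1 to 4.

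**Analysis.** Under Subject Disposition, the primary endpoint is the incidence and severity profile of adverse events on active drug against placebo. Proportions are compared by Fisher's exact test, with no formal hypothesis testing, and the stated expectation is that no signal will appear. Safety Analysis counts reported events and uses the highest severity when a patient has the same event more than once.

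**The concern.** The worsening route needs two intensities, one before and one after the first dose. The plan lists only the second. A patient who enters with nausea and still has it at Day 7 may or may not have an adverse event. The fields named in the protocol do not settle this, so each site must decide. The severity tables inherit the problem, because the highest grade is tabulated without reference to the grade at entry.

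The solicited list adds to this. It asks about five symptoms that are not named endpoints and leaves out those that are. The effects thought most likely for this oral product are therefore collected less systematically than rash or arthralgia.

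Safety is the primary endpoint, with 22 patients per arm. Error that falls equally on all arms does not favor either side in the usual sense, but it shrinks a true excess toward the no-signal result that the plan expects. In a safety comparison, that is the costly direction.

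**Working it through.** The plan gives no rate, power or sample size for the safety endpoint, so there is no figure of its own to reproduce. The check has three parts.

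**1. The definition against the recorded fields.**
- A new event after the first dose needs a start date. That is recorded, so this route works.
- Worsening of an ongoing condition needs intensity before and after. After dosing, the 1 to 4 grade is recorded. Before dosing, only name and dates are listed, and no visit is scheduled to grade symptoms. This route lacks its input.
- Laboratory changes need a baseline value. Table 2 schedules laboratory tests at Screening, and the Clinical Laboratory analysis section plans shifts from baseline. These are unaffected.

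**2. Named effects against the solicited list.**
- Named endpoints: nausea, vomiting, diarrhea. Anticipated effects: nausea, abdominal pain, flatus, diarrhea. Together these make five distinct symptoms.
- Solicited list: rash, pruritus, malaise, arthralgia, myalgia. Overlap: 0 of 5.
- Gap between scheduled assessments: 30 − 7 = 23 days. Dosing days inside it: 28 − 7 = 21, and 21/28 = 75%. This reads Day 30 as counted from Day 0, as the columns of Table 2 imply.

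**3. What the missing baseline grade could cost (illustration; all rates assumed).**

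Let b be the share of patients with the symptom at entry. Assume a true rate of new or worsened symptoms of 40% on one active arm and 10% on placebo, the same whether or not the symptom was present at entry. Take 22 per arm and a two-sided 5% Fisher test, with power found by full enumeration. Because the plan disclaims formal testing of this endpoint, power serves here only as a yardstick of sensitivity.

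- If sites count every ongoing symptom as an event, the observed rate in each arm is b + (1 − b)p.
- If sites count none of the ongoing symptoms, the observed rate is (1 − b)p.
- Either way the observed difference is (1 − b) × 30 points. At b = 0.4 it is 0.6 × 30 = 18 points.

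| b | All counted: rates | Power | None counted: rates | Power |
|---|---|---|---|---|
| 0 | 40% v 10% | 55% | 40% v 10% | 55% |
| 0.2 | 52% v 28% | 26% | 32% v 8% | 41% |
| 0.4 | 64% v 46% | 14% | 24% v 6% | 27% |
| 0.6 | 76% v 64% | 8% | 16% v 4% | 13% |

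The difference shrinks but does not vanish in any row.

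**A related, smaller point.** One secondary endpoint is "Proportion of subjects who develop renal failure, encephalopathy or pulmonary compromise". Encephalopathy is not an exclusion criterion, and its presence or absence is a planned subgroup factor, but no denominator is stated. If 30% had it at entry and 20% of the rest developed it (both assumed), the rate over all patients would be 0.20 × 0.70 = 14%, against 20% among those at risk.

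**The case against.** A reader might infer that the primary safety endpoint cannot separate drug effect from baseline illness. The documents do not support that. Allocation is randomized and double-blind with concurrent placebo, and the primary analysis compares active drug with placebo, so background illness is separated from drug effect at group level. New-onset events and laboratory shifts need no baseline symptom grade. The analysis text also counts reported events and never uses the treatment-emergent term. This answer stands, and it limits the harm to lost sensitivity. It does not close the gap, since pre-treatment events go to medical history and worsening is the only stated rule that brings them back as events.

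Two further inferences also fail. Gastrointestinal events are not left ungraded, because the 1 to 4 scale applies to every reported event. Nor do they rest on the open question alone: it supplements observation and spontaneous reports, the protocol calls for close monitoring for intolerance, and most patients are expected to start in hospital. The 21-day count is correct, but those days are not unobserved.

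It can also be said that the 0 to 3 scale is meant for systemic reactions, so the omission fits its title. That is fair, but no other solicited list covers the named endpoints. Medical history and physical examination at Screening, Day 7 and Day 30 provide some source material for judging worsening, though no required grade. The case report form is not among the documents and may hold one.

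On encephalopathy, the endpoint's wording already implies new onset, and Child-Pugh is scheduled at Screening. If prevalence at entry is similar across arms, the dilution leaves the risk ratio unchanged. What remains is a clarification.

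**Conclusion.** The point holds as a loss of sensitivity in the primary safety endpoint, chiefly for gastrointestinal effects. Worsening of symptoms present at entry cannot be classified reproducibly from the fields the protocol lists, and none of the five named or anticipated gastrointestinal effects is solicited. It does not hold as a claim that the arms cannot be compared or that the treatment-emergent definition is unusable as a whole, since only its worsening route lacks an input.

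The size depends on how many patients have the symptom at entry, which the documents do not give. Over an assumed range of 20% to 60%, power falls from 55% to between 41% and 13% if ongoing symptoms are left out, and to between 26% and 8% if they are all counted. These figures also rest on the assumed 40% and 10% rates and on every site following the same rule. They show direction and scale and are not estimates for this trial.

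**What to change.** - At Day 0 before the first dose, and again at Day 7 and Day 30, ask about and grade nausea, vomiting, diarrhea, abdominal pain and flatus. Use the existing Grade 1 to 4 scale, with 0 for absent, so that no event carries two severity scores. Add the Day 0 mark to Table 2.
- Record intensity for ongoing pre-treatment events on the medical history page.
- Report gastrointestinal endpoints by arm as new or worsened by at least one grade from Day 0, alongside all reported adverse events.
- As a minor clarification, report encephalopathy as new onset among patients free of it at entry, with worsening shown separately, from baseline data already collected.

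The cost is a few extra form lines at visits already scheduled. Solicited gastrointestinal rates will be higher in all arms and will not compare directly with spontaneously reported rates in earlier studies. Keeping the tables of all reported events alongside does not remove that limit, so the report should state how the events were collected.
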